## Background and Rationale

[figure not shown]
- Provide background on unanswered question(s) the study is attempting to answer (do not exceed one page)

Primary insomnia (PI) sufferers typically complain of such daytime impairments as reduced attention, concentration, memory and global mental acuity. Moreover, epidemiological studies have shown PI contributes to reduced productivity, work and traffic accidents, and serious falls among the elderly. Despite such findings, laboratory-based efforts to corroborate the cognitive complaints of PI sufferers have produced mixed results. Indeed, many studies comparing PI sufferers with non-complaining normal sleepers across a range of neuropsychological tests have failed to show any relative deficits among the PI group. Such findings, in turn, has led to the impression that PI patients cognitive complaints may be over-stated and result from their attentional bias toward minor cognitive errors, dysfunctional beliefs about the impact of insomnia on functioning or excessive self focus rather than to any measurable daytime impairment.

However, many previous such studies were underpowered due to small sample sizes and employed neuropsychological tests designed for detecting impairment resulting from brain disease/damage rather than the more subtle albeit significant impairments of which PI patients complain. In recent research, we and others have shown that PI sufferers do, indeed, show greater deficits (slower and more variable reaction times) particularly on complex switching attention tasks. Moreover, there is some preliminary evidence that the subgroup of PI sufferers with elevated levels of physiological hyperarousal are most prone to suffer from neuro-cognitive performance deficits than are matched groups of PI sufferers who are not physiologically hyperaroused and normally alert individuals without insomnia. For example, Fernandez-Mendoza recently showed that PI sufferers with a hyperarousal pattern suggested by their objective short sleep duration on serial polysomnograms (PSG) performed more poorly on a complex switching attention task than did both normal sleepers and PI sufferers with normal objective sleep durations.

In our efforts to follow up on this latter work, we recently examined the error rates of alert and sleepy PI sufferers and normal sleepers across a series of simple and complex reaction time tasks. We employed age and gender matched samples of PI (N=89) sufferers and normal sleepers-NS (N=95). Participants underwent three nights of PSG followed by daytime testing with a four-trial Multiple Sleep Latency Test-MSLT. The PI and NS groups were each subdivided into "alert" (e.g., MSLT mean onset latency > 8 minutes) and "sleepy" (e.g., MSLT mean onset latency  $\leq$  8 minutes) subgroups to allow for testing the main and interaction effects of participant type and level of alertness. "Alert" participants had longer MSLT latencies than "sleepy" participants (12.7 vs. 5.4 minutes). PI sufferers had fewer correct responses on performance testing than did NS. However, as shown by the adjacent, figure we found a significant group x alertness interaction ( $p = .0013$ ) with greater error rates occurring among alert (hyperaroused) PI sufferers (Mean=4.5 $\pm$ 3.6 errors per trial) than among alert NS (Mean=2.6 $\pm$ 1.9 errors per trial). This was particularly true for the more complex switching attention task.

Our work along with that of Fernandez-Mendoza serve to confirm that PI sufferers have measurable objective neuro-cognitive deficits and provide some preliminary suggestion for the types of testing approaches that should be used to detect them. The identification of tests sensitive to PI sufferers' cognitive deficits are particularly relevant for testing the effects of current and future insomnia therapies on patients' objective daytime functioning. Measures of daytime dysfunction can and should serve as endpoints for assessing benefits and detriments of insomnia therapies. In addition, our recent work suggests that subgroups of PI sufferers may differ in their daytime deficits, with those showing physiological hyperarousal being most prone to make errors. This finding suggests that different types or doses of treatment may be needed to reverse the daytime impairments of the hyperaroused and non-aroused PI patients. However, our line of research would benefit by replication and extension findings to (1) further confirm the detrimental effects of physiological hyperarousal on PI sufferer's neuro-cognitive functioning; and (2) identify a broader range of tests that can be used for assessing diurnal cognitive impairments in both physiologically hyperaroused and lesser aroused PI groups. The current project will address these aims.

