# A

## Objectives

- List the objectives to correspond directly with the listed hypotheses:

**Aim 1:** To compare the performances of hyperaroused PI sufferers and normally alert normal sleepers across a battery of computer-administered neuro-cognitive reaction time tests.

**Aim 2:** To examine the relative sensitivities of a range of simple and complex reaction time tests for discriminating PI sufferers from non-complaining normal sleepers.

**Aim 3 (Exploratory):** To examine the degree to which measures of the macro- and micro-architecture of sleep account for the daytime performance deficits shown by hyperaroused PI sufferers

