## Study Design/Clinical Plan

- Provide a concise overview stating the type of experimental design

This study will use a matched-groups cross-sectional experimental design. Age and gender matched groups of hyperaroused PI sufferers and non-complaining normal sleepers (NS) will be recruited and enrolled. A comprehensive screening process that includes structured sleep and psychiatric interviews, screening questionnaires, vitals, urine pregnancy test, medical history, and diagnostic PSG will be used to determine eligible subjects. Our screening procedures and selection criteria are designed to allow us to identify and enroll hyperaroused PI sufferers and normally alert normal sleepers. PI sufferers enrolled will meet Research Diagnostic Criteria for insomnia disorder, score  $> 14$  on the Insomnia Severity Index, report insomnia for  $> 3$  months, have sleep difficulties  $\geq 3$  nights per week, score  $\leq 3$  on the Epworth Sleepiness Scale (ESS), score  $\geq 29$  on the Hyperarousal Scale and report an inability to nap in the daytime. The normal sleepers enrolled will report general satisfaction with sleep and no sleep/wake complaints, score  $\leq 10$  on the ESS, score  $< 25$  on the Hyperarousal Scale, and deny a practice of routine daytime napping. Those excluded will have: (a) a sleep-disruptive medical condition (e.g., rheumatoid arthritis); (b) a current major psychiatric (Axis I) condition on the basis of a Structured Clinical Interview for Psychiatric Disorders (SCID); (c) sedative hypnotic dependence and unwillingness/inability to abstain from these medications while in the study; (d) use of anxiolytics, antidepressants, or any other psychotropic medication; or (e) an apnea/hypopnea index (AHI)  $> 5$  or a periodic limb movement-related arousal index  $> 15$  during on screening PSG that includes a full sleep montage to allow for detection/diagnosis of sleep-disordered breathing and PLMD. Additionally, self-described NS who meet criteria for any sleep disorder and those insomnia sufferers who meet criteria for a comorbid sleep disorder in addition to PI will also be excluded.

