# A

factorial analysis. Although our statistical model could also include "trials" as a factor, we have chosen to limit the complexity of our analyses by excluding this factor and using mean values of each of our performance measures across trials for each participant in our analyses. To further simplify our analyses we will compute mean values of our 5 dependent measures for the three simple tests and another set of mean values of these dependent measures for our three complex tests and use those composite means in all planned analyses.

Before conducting tests of the study hypotheses, we will conduct a number of preliminary 2 (PI vs. NS) x 2 (alert vs. sleepy) x 2 (simple vs. complex test) ANOVAs and cross tabs analyses to determine if the various "cells" of our study include participants who do not differ significantly in terms of their mean ages, years of education, gender compositions and racial/ethnic compositions. If study "cells" are found to differ significantly on any of these variables, those variables will be used as covariates in statistical models designed to test study hypotheses. If study cells do not differ in regard to these variables we will use unadjusted statistical models to test study hypotheses.

For study hypotheses 1 & 2, we will conduct 2 (PI vs. NS) x 2 (simple vs. complex test) MANOVAs/MANCOVAs analyses to test for statistical significance across the multiple performance measures derived from the neuro-cognitive test battery. If the MANCOVA/MANOVA shows significant results, univariate ANCOVAs/ANOVAs will be conducted to tests for similar significant effects for each individual performance measure (i.e., mean reaction time; within subject standard deviations for reaction time; error responses).

Hypothesis 1 will be tested via examination of the main effect of the *group factor* (PI vs. NS) in these analyses. Findings showing significantly slower and more variable reaction times, fewer correct responses and higher error rates in the hyperaroused PI group will support this hypothesis. Elimination of these statistical differences in repeat analyses that use hyperarousal scale scores as a covariate will confirm the role of hyperarousal in explaining the observed group differences.

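### The Background promises findings on hyperarousal itself and on lesser aroused PI, but the design supports only a contrast of hyperaroused PI with normal sleepers

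*Combined protocol and SAP*

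**What the plan says.** All references are to the combined protocol and SAP.

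- **Background and Rationale.** The work needs, first, to "further confirm the detrimental effects of physiological hyperarousal on PI sufferer's neuro-cognitive functioning" and, second, to find a broader range of tests for "assessing diurnal cognitive impairments in both physiologically hyperaroused and lesser aroused PI groups. The current project will address these aims".
- **Objectives, Aim 2.** The aim is to compare "simple and complex reaction time tests for discriminating PI sufferers from non-complaining normal sleepers", with no restriction on the kind of PI. Hypothesis 2, its counterpart, is restricted to hyperaroused PI.
- **Study Design/Clinical Plan.** Screening is "designed to allow us to identify and enroll hyperaroused PI sufferers and normally alert normal sleepers". PI must "score $\geq 29$ on the Hyperarousal Scale", have an Epworth score of 3 or less, "and report an inability to nap in the daytime". Normal sleepers must "score $< 25$ on the Hyperarousal Scale".
- **Power Considerations.** Planned enrolment is 82 hyperaroused PI and 82 NS. There is no other group.
- **Statistical Plans.** The hypothesis models have two factors, group and test difficulty. If the group difference disappears when the Hyperarousal Scale score is added as a covariate, this is to be taken as confirmation of hyperarousal's role. That rule is given for Hypothesis 1 and again for Hypothesis 2. Covariates are chosen from a balance check described as "preliminary 2 (PI vs. NS) x 2 (alert vs. sleepy) x 2 (simple vs. complex test) ANOVAs" with cross tabulations.

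**The concern.** The stated scope is wider than the enrolled population. Both precedents in the Background separated PI by arousal: one compared short and normal objective sleepers within PI, and the pilot crossed PI/NS with alert/sleepy. This design has neither a lesser aroused PI group nor a hyperaroused NS group.

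Two conclusions are at stake. A positive Hypothesis 1 could be reported as an effect of hyperarousal when insomnia would explain it equally well. Test sensitivities found in hyperaroused PI could be carried over to other PI, although the pilot's own group by alertness interaction (p = .0013) suggests that the deficit varies between subgroups. The Background proposes such measures as endpoints for insomnia therapies, so the distinction has practical weight.

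**Working it through.** **1. The plan's own power figures.** Inputs are the means and SDs in Power Considerations, with 82 per group and alpha .05. Sidedness is not stated; two-sided reproduces the figures and one-sided does not. With d = difference/SD, power ≈ Φ(d·√(82/2) − 1.96), where √41 = 6.403.

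| Measure | d | Power (normal) | Stated |
|---|---|---|---|
| Errors | (4.46 − 2.60)/3.45 = 0.539 | .932 | .93 |
| Correct responses | (77.5 − 75.7)/3.74 = 0.481 | .869 | .87 |
| Latency | (470.6 − 420.8)/112.1 = 0.444 | .812 | .81 |
| Complex-test latency | (496.65 − 438.14)/133.4 = 0.439 | .802 | .80 |
| Simple-test latency | (247.9 − 226.4)/66.8 = 0.322 | .540 | .54 |

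The noncentral t gives .929, .865, .807, .797 and .535. The arithmetic is sound. At 82 per group all of it concerns PI against NS; none concerns hyperaroused against lesser aroused PI.

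**2. Promised against enrolled.**

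| Question in the Background | Contrast needed | In the design? |
|---|---|---|
| Do hyperaroused PI perform worse than NS? | Hyperaroused PI v NS | Yes |
| Which tests discriminate in hyperaroused PI? | Test types within that contrast | Yes |
| Does hyperarousal, apart from insomnia, impair PI? | Hyperaroused v lesser aroused PI | No |
| Which tests work in lesser aroused PI? | Lesser aroused PI v NS | No |

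**3. Can the covariate separate insomnia from hyperarousal?** Every PI score is at least 29 and every NS score is below 25, so adjustment compares the groups at a common score that they never share. It also inflates the variance of the group effect. With equal groups, mean gap g and within-group SD s, R² between group and score is (g/2)²/[(g/2)² + s²], and the variance inflation is 1/(1 − R²) = 1 + (g/2)²/s².

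The documents give neither g nor s. I assume g from 8 to 20 points and s from 2 to 6. I also leave the adjusted error difference at 1.86 and the residual SD at 3.45, which means hyperarousal explains nothing.

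| g | s | R² | Inflation | Power, errors |
|---|---|---|---|---|
| 8 | 6 | .308 | 1.44 | .82 |
| 8 | 4 | .500 | 2.00 | .69 |
| 15 | 4 | .779 | 4.52 | .37 |
| 20 | 4 | .862 | 7.25 | .25 |
| 20 | 2 | .962 | 26.0 | .10 |

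For the first row: 0.539 × 6.403/√1.444 = 2.87, and Φ(2.87 − 1.96) = .82. The chance of losing significance is therefore .18 to .90 (1 − .82 to 1 − .10), against .07 without the covariate, even though hyperarousal plays no part. The plan would read that loss as confirmation.

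**4. The balance check.** Alert/sleepy is neither an eligibility criterion nor a factor in the hypothesis models. Every participant takes both simple and complex tests, so test difficulty cannot define different sets of people. The comparison relevant to choosing covariates is PI against NS.

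**The case against.** The strongest reply is that the Background is narrative and the operative text is already narrow. Aims 1 and 3, both hypotheses, the enrolment plan and the Hypothesis 1 power table all refer to hyperaroused PI, and the missing adjective in Aim 2 looks like a drafting slip. Enrolling an enriched group is a legitimate choice. This largely stands, and it makes the point one of scope rather than of a faulty primary test. It does not dispose of the Background's explicit commitment to lesser aroused PI. Nor does it touch the covariate rule, which is operative text and is the plan's only means of isolating hyperarousal.

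A second reply is that eligibility has no MSLT cut, that everyone has a four-trial MSLT, and that alert/sleepy cells could be formed afterwards. That is true: the complete separation is shown for the self-report scale, not for the MSLT measure behind the pilot interaction. But no test within PI is planned. As an illustration, an even 41/41 split of the PI group, with a difference as large as the stated PI–NS difference, would have power of only Φ(0.539·√20.5 − 1.96) = .69 for errors and .52 for latency.

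Three stronger readings are tempting and not supported:

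- A reader might infer that only the most hyperaroused PI are admitted. The documents give cut-offs but no score distribution.
- A reader might infer that neither Background aim can be addressed at all. The hyperaroused PI v NS difference can be replicated, and a wider battery can be evaluated within it.
- A reader might put a figure on the diluted effect in PI as a whole. The documents give neither the share of lesser aroused PI nor the size of their deficit. They call hyperaroused PI most prone to deficits, which does not mean that others have none.

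**Conclusion.** The point holds as a mismatch between stated scope and design. The trial can answer whether hyperaroused PI differ from NS and which tests show it, with the stated powers. It cannot address lesser aroused PI, and it cannot attribute a difference to scale-defined hyperarousal rather than insomnia. Both conclusions follow from the eligibility cut-offs alone and need no outside figure.

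The size of the covariate problem does rest on assumptions. Over the assumed gaps and SDs, power for an unchanged error difference is .82 to .10. The lack of overlap holds whatever those values are. The alert/sleepy factor in the balance check is a lesser inconsistency, but the check decides which covariates enter the hypothesis models, so it should be settled before analysis.

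**What to change.** 1. **Background and Aim 2.** Limit both to hyperaroused PI against NS, matching Hypothesis 2, and remove lesser aroused PI from what the project will address.
2. **Statistical Plans, Hypotheses 1 and 2.** State that a Hypothesis 1 difference is the joint effect of insomnia and hyperarousal and does not extend to other PI. Replace both statements that loss of significance confirms the role of hyperarousal with wording that calls the covariate analysis exploratory and unable to separate the two. These changes must be made together, or the text would contradict itself.
3. **Balance check.** Compare PI with NS, the two groups in the hypothesis models, and drop the alert/sleepy factor.

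No participants, procedures or hypothesis tests change, and the sample size stands. The cost is narrower claims. Keeping the wider claims would instead need a lesser aroused PI group, or the full range of arousal within PI, with its own sample-size justification.

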# A

## Objectives

- List the objectives to correspond directly with the listed hypotheses:

**Aim 1:** To compare the performances of hyperaroused PI sufferers and normally alert normal sleepers across a battery of computer-administered neuro-cognitive reaction time tests.

**Aim 2:** To examine the relative sensitivities of a range of simple and complex reaction time tests for discriminating PI sufferers from non-complaining normal sleepers.

**Aim 3 (Exploratory):** To examine the degree to which measures of the macro- and micro-architecture of sleep account for the daytime performance deficits shown by hyperaroused PI sufferers

## Hypothesis

- List the clinical Hypotheses in order of priority:

**Hypothesis 1:** Hyperaroused PI sufferers will show greater performance deficits (slower reaction times; fewer correct responses and more error responses) across repeated daytime testing trials than will age- and gender-matched normal sleepers.

**Hypothesis 2:** Complex reaction time tasks that require executive function, ability to switch attention, and higher order memory function will show greater discrimination of hyperaroused PI sufferers and normal sleepers on measures of mean reaction time, correct response rates and error rates than will simple reaction time tasks.

**Exploratory Aim 3:** To determine the possible sleep deficiencies/mechanisms that contribute to the relative daytime deficits in the hyperaroused PI subgroups we will test measures of sleep continuity (sleep and wake time) and the macro-architecture (sleep stage percentages) and micro-architecture (NREM sleep EEG spectral measures) derived from PSG on nights preceding daytime testing as covariates in study analyses to determine the degree to which they account for observed group differences.

## Study Design/Clinical Plan

- Provide a concise overview stating the type of experimental design

This study will use a matched-groups cross-sectional experimental design. Age and gender matched groups of hyperaroused PI sufferers and non-complaining normal sleepers (NS) will be recruited and enrolled. A comprehensive screening process that includes structured sleep and psychiatric interviews, screening questionnaires, vitals, urine pregnancy test, medical history, and diagnostic PSG will be used to determine eligible subjects. Our screening procedures and selection criteria are designed to allow us to identify and enroll hyperaroused PI sufferers and normally alert normal sleepers. PI sufferers enrolled will meet Research Diagnostic Criteria for insomnia disorder, score  $> 14$  on the Insomnia Severity Index, report insomnia for  $> 3$  months, have sleep difficulties  $\geq 3$  nights per week, score  $\leq 3$  on the Epworth Sleepiness Scale (ESS), score  $\geq 29$  on the Hyperarousal Scale and report an inability to nap in the daytime. The normal sleepers enrolled will report general satisfaction with sleep and no sleep/wake complaints, score  $\leq 10$  on the ESS, score  $< 25$  on the Hyperarousal Scale, and deny a practice of routine daytime napping. Those excluded will have: (a) a sleep-disruptive medical condition (e.g., rheumatoid arthritis); (b) a current major psychiatric (Axis I) condition on the basis of a Structured Clinical Interview for Psychiatric Disorders (SCID); (c) sedative hypnotic dependence and unwillingness/inability to abstain from these medications while in the study; (d) use of anxiolytics, antidepressants, or any other psychotropic medication; or (e) an apnea/hypopnea index (AHI)  $> 5$  or a periodic limb movement-related arousal index  $> 15$  during on screening PSG that includes a full sleep montage to allow for detection/diagnosis of sleep-disordered breathing and PLMD. Additionally, self-described NS who meet criteria for any sleep disorder and those insomnia sufferers who meet criteria for a comorbid sleep disorder in addition to PI will also be excluded.

Once consented, all participants will undergo screening procedures mentioned above. Those passing screening procedures will be scheduled for two consecutive nights of home-based PSG followed immediately by a daytime testing protocol. The nighttime PSG montage will include bilateral central and occipital referential EEG channels (C4 and O1, each referenced to M1 + M2), electro-oculogram (EOG, referenced to contralateral mastoid), submentalis electromyogram (EMG), and EKG. The PSGs will be used to derive sleep measures to address our exploratory Aim 3.

The daytime protocol will include a 4-trial Multiple Sleep Latency Test (MSLT) along with 4-trials of a computer –

# A

administered battery of reaction time tasks. The assessment protocol will start two to three hours after participants' respective morning rising times and will begin with a battery of the neuro-cognitive testing followed by an MSLT nap. Per standard MSLT procedures, the daytime testing will be scheduled so the four performance testing and sleepiness assessment trials occur two hours apart. All daytime testing will be conducted under the supervision of trained laboratory technologists. Immediately prior to initiating daytime testing, participants' electrodes worn for the previous night's PSG will be checked and readjusted if necessary. Participants will be supervised between trials to prevent unscheduled sleep episodes. PSG electrodes will be worn for the entire day of laboratory testing and will not be removed until after the final trial is completed. Once the fourth performance/MSLT trial is completed and electrodes are removed, the participant will be allowed to leave the laboratory.

The neuro-cognitive test battery will include a 38 minute battery of simple and complex tests selected from CANTAB® Tests made available from Cambridge Cognition. The simple and complex tests will be presented in alternating order to control for the effects of fatigue on subjects' test performances. Among the simple tasks will be the Simple Reaction Time Test, Big Circle/Little Circle Test and Choice Reaction Time Test. These tests all provide measures of reaction time and motor speed but involve minimal cognitive load. The more complex tests will include the Rapid Visual Information Processing Test, The Spatial Working Memory Test and the Attention Switching Test. These latter tests collectively assess reaction time, attention, concentration, memory, and executive function, and thus, involve more cognitive load making them more sensitive to the deficits PI patients manifest. Both the simple and complex tests provide measures of respondents' mean reaction times, variability in reaction times across stimulus presentations, counts of correct responses, and counts of errors of omission and commission. These data are provided for each respondent for each trial allowing for analyses of respondents performances on a trial x trial basis as well as their average performances across trials.

Following each administration of the performance testing, the participant will be placed in a laboratory bedroom for the MSLT trial. Most aspects of the standard protocol will be followed in conducting the MSLT. However, conservative MSLT criteria rather than contemporary clinical criteria will be used to define the sleep latency for each nap. Specifically, sleep latency will be defined as the time between the beginning of the nap trial and either the first three consecutive 30-second epochs of stage 1 sleep or the first 30-second epoch of any other sleep stage. If no sleep occurs, the trial will end at 20 minutes and a sleep latency of 20 minutes will be assigned. To minimize carry-over effects from one nap to the next, each nap trial will be discontinued 5 minutes after the sleep onset criterion is met.

Once all participants have completed the study protocol we will compare our groups of PI and NS in regard to their mean sleep onset latencies shown on the four MSLT naps to assure the groups do not differ in regard to their observed levels of daytime alertness. The dependent measures we plan to use in study analyses include: (1) mean reaction time per trial for each test; (2) # of correct responses per trial for each test; (3) # of errors of commission per trial for each test; (4) # of errors of omission per trial for each test; and (5) total # of errors per trial for each test. Our analysis plan below outlines how these measures will be used to test our study aims and hypotheses.

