Hypothesis 2 will be tested via examination of the interaction of the *group factor* (PI vs. NS) and *test difficulty factor* (simple vs. complex) in these analyses. This finding coupled with a posteriori comparisons showing that PI participants have significantly poorer performances than do NS only on the complex tasks will support this hypothesis. Again, elimination of these statistical differences in repeat analyses that use each participant's hyperarousal scale score as a covariate will confirm the role of hyperarousal in explaining the observed group differences on complex tasks.

Our Exploratory Aim will require us to derive a variety of measures from the PSGs conducted on the two nights preceding daytime testing. Following the AASM Scoring Manual guidelines we will score these PSG records and obtain measures of total sleep time, sleep onset latency, wake time after sleep onset, sleep efficiency, and percentages of stages N1, N2, N3, and R for each night. We also will de-artifact each night and then perform a Fast Fourier Transform and subsequent sleep EEG spectral analysis as per our previously published reports to derive NREM absolute and relative spectral power measures in the delta, theta, alpha, sigma, beta and gamma bandwidths. Once these measures are derived for each night, we will compute mean values of these measures for the two PSG nights and then enter those into multivariate regression analyses to determine which measures predict each of the five performance variables used as dependent measures. Those found to be predictive of performance indices will be entered as covariates in the above factorial analyses to determine if any such measures account for the anticipated relative deficits shown by the insomnia group vis a vis the normal group. Since we will anticipate group differences only on the 5 performance measures derived from the set of complex tests, we will plan to test our sleep measures as covariates only in one-way group comparisons using response latency, correct response rate, and error rate data acquired from the complex tests as dependent measures in these analyses. We, thus, will conduct and 5 ANCOVA analyses in which the sleep measures are tested as covariates with each of the 5 performance measures obtained from the complex reaction time tests.

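### Alternating three simple and three complex tests only partly controls fatigue; the plan should state the sequence and reverse the starting class across the four trials

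*Combined protocol and SAP*

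**What the plan says.** In the combined protocol and SAP, Study Design/Clinical Plan describes the testing: "The neuro-cognitive test battery will include a 38 minute battery of simple and complex tests". The tests are named by class. For the simple class: "Among the simple tasks will be the Simple Reaction Time Test, Big Circle/Little Circle Test and Choice Reaction Time Test". For the complex class: "The more complex tests will include the Rapid Visual Information Processing Test, The Spatial Working Memory Test and the Attention Switching Test". On order, the only statement is: "The simple and complex tests will be presented in alternating order to control for the effects of fatigue on subjects' test performances". The battery is given four times in the day; the schedule is set so that "the four performance testing and sleepiness assessment trials occur two hours apart".

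Statistical Plans drops trial as a factor, "using mean values of each of our performance measures across trials for each participant in our analyses", and then averages the three simple tests into one composite and the three complex tests into another for each measure. On the second hypothesis it says: "Hypothesis 2 will be tested via examination of the interaction of the *group factor* (PI vs. NS) and *test difficulty factor* (simple vs. complex". Support also requires follow-up contrasts in which PI do worse than NS on the complex tasks alone.

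The documents do not say which class starts, whether the start is fixed or varies across trials or participants, or whether order is counterbalanced or randomised. No position or order term appears in the analysis.

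**The concern.** Difficulty is a within-person factor, so anything that differs systematically between the simple and complex tests besides difficulty enters the difficulty contrast. Position in the battery is one such thing. An alternating run of six tests cannot give both classes the same average position, so a repeated order leaves a residual offset. The planned averaging over trials and tests neither removes nor reveals it. With one order for everyone, each test would keep the same position throughout, and position could not be separated from test class afterwards.

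Hypothesis 2 rests on whether the PI deficit is larger on complex than on simple tests. If PI participants lose speed or accuracy over the battery faster than NS, part of that extra loss falls unevenly on the later class. Complex tests placed later would inflate the interaction, and complex tests placed earlier would mask it. Because the starting class is not given, the direction cannot be predicted from the plan.

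**Working it through.** **Inputs.** Battery length 38 minutes, three tests per class, four trials (Study Design/Clinical Plan). Latencies for PI, NS and SD (Power Considerations): complex 496.65, 438.14, 133.4 ms; simple 247.9, 226.4, 66.8 ms; 82 per group, alpha .05. Assumed, because the documents give none: fatigue slopes, no breaks between tests, and the within-person correlation between the two composites.

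**1. The plan's own figures.** The standard error of a group difference is SD × √(2/82).
- Complex: 58.51 / (133.4 × 0.1562) = 2.81; two-sided power Φ(2.81 − 1.96) = 0.80, as stated.
- Simple: 21.5 / (66.8 × 0.1562) = 2.06; power Φ(2.06 − 1.96) = 0.54, as stated.

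So the latency inputs are read as the plan used them. The power figures are not in dispute on this point.

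**2. Position offset under a repeated order.** The class that starts holds positions 1, 3 and 5, mean (1+3+5)/3 = 3. The other holds 2, 4 and 6, mean (2+4+6)/3 = 4. The gap is one position.

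In minutes, pair each earlier-class test (length a) with the test that follows it (length b). Their midpoints are (a+b)/2 apart. Averaged over three pairs, the offset is (total length)/6 = 38/6 = 6.33 minutes, whatever the individual test lengths.

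For comparison, running all of one class first gives mean positions 2 and 5, a gap of three positions (19 minutes if tests within a class are equally long). Alternation therefore removes about two thirds of the imbalance.

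**3. Effect on the contrasts.** Suppose latency rises linearly by f_PI or f_NS ms per minute on task, with the same slope for both classes within a group. Let D be complex minus simple mean time in the battery: +6.33 if simple tests start, −6.33 if complex tests start.
- Difficulty main effect: shifted by D × (f_PI + f_NS)/2.
- Group-by-difficulty interaction: shifted by D × (f_PI − f_NS).
- Equal slopes: the interaction shift is zero, however steep the fatigue.
- Group main effect: the six positions average 3.5 whichever class starts, so the position offset does not bias it.

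**4. Size on the plan's scale.** The planning interaction is (496.65 − 438.14) − (247.9 − 226.4) = 58.51 − 21.50 = 37.01 ms.

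| Assumed extra PI slowing | Shift in interaction | Share of 37.01 ms |
|---|---|---|
| 0.5 ms/min | 0.5 × 6.33 = 3.2 ms | 9% |
| 1 ms/min | 1 × 6.33 = 6.3 ms | 17% |

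**5. Size against sampling error.** The standard error of the interaction is √(133.4² + 66.8² − 2r × 133.4 × 66.8) × √(2/82), where r is the assumed correlation. It is 23.3 ms at r = 0, 18.0 ms at r = 0.5 and 14.0 ms at r = 0.8. Shifts of 3.2 to 6.3 ms are then 0.14 (3.2/23.3) to 0.45 (6.3/14.0) standard errors.

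**6. After reversing the start on two of the four trials.** Each class averages (3+4)/2 = 3.5 within each person, and D averages (+6.33 − 6.33)/2 = 0. The shifts in the difficulty main effect and the interaction under step 3 are zero.

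**The case against.** A reader might infer that the plan uses one rigid order in every trial, that alternation fails to control fatigue, and that Hypothesis 2 is therefore confounded with time on task. The documents do not support that reading.

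- **The order is not given.** They say only that the classes alternate. A start that varies across trials or participants is not excluded; it is simply not stated. This stands, and the offset is conditional on a repeated order.
- **Alternation does much of the work.** It cuts the gap from three positions to one. This stands.
- **Common fatigue cancels.** Hypothesis 2 uses the interaction, and both groups would meet each class at the same positions. This stands. Bias needs fatigue that differs by group, or that is not additive across test classes.
- **No basis for a differential is given.** The plan selects PI participants with Epworth scores of 3 or less and NS with 10 or less, and compares the groups on sleep latency in the daytime nap test. Sleepiness is not time-on-task fatigue, so this does not rule out a difference in slopes, but neither its presence nor its direction is documented. PI complaints of reduced attention and concentration, described in Background and Rationale, make one plausible and no more.
- **Steep slopes fit the plan's figures badly.** An extra 2 ms per minute would mean 2 × 38 = 76 ms of added PI slowing by the end of the battery, more than the whole planned complex-task difference of 58.51 ms. This is why the illustration stops at 1 ms per minute. At 0.5 to 1 ms the shift is under half a standard error and unlikely to decide Hypothesis 2 alone.
- **The illustration covers latency only.** Nothing is quantified for correct responses or errors, which are also outcomes.

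These objections limit the size and certainty of the point. They do not supply the missing sequence or remove the offset if one order is repeated.

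**Conclusion.** The point holds in a limited form. Alternating three and three reduces position imbalance but cannot remove it within a single trial, and the plan describes nothing that would remove it across trials. The offset of one position, or 6.33 minutes, is exact for any repeated alternating order without breaks. Its effect on Hypothesis 2 is conditional: zero if fatigue is additive and equal in both groups, and of unknown size and sign otherwise. The shift of about 3 to 6 ms rests on slopes that were assumed, not found in the documents. This is an inexpensive design improvement, not evidence that the Hypothesis 2 test is invalid. It is worth making before testing starts, since a fixed order cannot be undone in the analysis.

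**What to change.** State the test sequence in Study Design/Clinical Plan and reverse the starting class across each participant's four trials, for example simple-first on trials 1 and 4 and complex-first on trials 2 and 3, using the same scheme in both groups. Running the whole sequence backwards on the reversed trials is a simple way to do it: a test at position p moves to 7 − p, so each individual test averages 3.5 as well as each class. Giving half of each group the mirror scheme (complex-first on trials 1 and 4) is optional, because the within-person reversal already equalises mean position.

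The change has limits. It cancels a linear position trend whose slope is common to both test classes. It does not cancel every nonlinear trend, or fatigue that grows with cognitive load. Nor does it remove differential fatigue from the separate PI-versus-NS contrasts on each class; it places both classes at the same average point in the battery.

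The cost is that technologists run two launch orders instead of one. No tests, testing time or participants are added, and the stated sample size and power are unchanged.
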